**5.1 Device Name : PTSD Coach**

**Describe the device to be used.**

VA's PTSD Coach mobile app

**Manufacturer** VA

**IDE Exemption**

Y This is a legally marketed device being used in accordance with its labeling.

**6. Drugs, Reagents, or Chemicals and Devices**

**a) Please list in the table below all investigational drugs, reagents or chemicals to be administered to participants.**

**b) Please list in the table below all commercial drugs, reagents or chemicals to be administered to participants.**

**7. Medical Equipment for Human Subjects and Laboratory Animals**

**If medical equipment used for human patients/participants is also used on animals, describe such equipment and disinfection procedures.**

NA

**8. Participant Population**

**a) State the following: (i) the number of participants expected to be enrolled at Stanford-affiliated site(s); (ii) the total number of participants expected to enroll at all sites; (iii) the type of participants (i.e. students, patients with certain cancer, patients with certain cardiac condition) and the reasons for using such participants.**

(i) 130 eligible VA Palo Alto Health Care System primary care patients  
(ii) 260 eligible VA primary care patients in total in the study (the VA Syracuse site will recruit 130 or more primary care patients depending on recruitment efforts at Palo Alto).  
(iii) All primary care patients will be Veterans who have screened positive for posttraumatic stress disorder (PTSD). The intervention being tested is intended to address PTSD in Veterans who are treated in VA primary care settings.

**b) State the age range, gender, and ethnic background of the participant population being recruited.**

All participants will be 18 years old or older. Both genders will be included as will patients of all ethnic backgrounds. However, all participants will be English-speaking and English-literate to ensure proper and consistent comprehension of both written materials and instructions.

**c) State the number and rationale for involvement of potentially vulnerable subjects in the study (including children, pregnant women, economically and educationally disadvantaged, decisionally**

**Title :** An RCT of a Primary Care-Based PTSD Intervention: Clinician-Supported PTSD Coach  
**Approval Period:** Draft

**impaired, homeless people, employees and students). Specify the measures being taken to minimize the risks and the chance of harm to the potentially vulnerable subjects and the additional safeguards that have been included in the protocol to protect their rights and welfare.**

As this is a pragmatic effectiveness trial, we will include as broad a swath of the VA primary care patient population as possible by limiting exclusion criteria so an unknown number of potentially vulnerable participants may participate, including pregnant women, economically and educationally disadvantaged, and homeless Veterans. We will not include children and the decisionally impaired. All participants will be involved in PC-MHI treatment with a licensed clinician.

- d) If women, minorities, or children are not included, a clear compelling rationale must be provided (e.g., disease does not occur in children, drug or device would interfere with normal growth and development, etc.).**

Women and minorities will be included. Minors will not be included, as this is a study of adults.

- e) State the number, if any, of participants who are laboratory personnel, employees, and/or students. They should render the same written informed consent. If payment is allowed, they should also receive it. Please see Stanford University policy.**

NA

- f) State the number, if any, of participants who are healthy volunteers. Provide rationale for the inclusion of healthy volunteers in this study. Specify any risks to which participants may possibly be exposed. Specify the measures being taken to minimize the risks and the chance of harm to the volunteers and the additional safeguards that have been included in the protocol to protect their rights and welfare.**

All participants will be VA primary care patient with PTSD symptoms.

- g) How will you identify and recruit potential participants about the research study? (E.g., by: Honest Broker or other <https://researchcompliance.stanford.edu/participantengagement> Research Participation services; chart review; treating physician; ads). All final or revised recruitment materials, flyers, etc. must be submitted to the IRB for review and approval before use. You may not contact potential participants prior to IRB approval. See Advertisements: Appropriate Language for Recruitment Material.**

Recruitment of participants will involve 2 methods:  
1) Direct in person referral from clinical staff on the patient's health care team (PACT) in the primary care setting.  
2) Review of charts for patients screening positive for PTSD as part of standard practice (with approved waiver of authorization for recruitment) or who have had an primary care encounter in which PTSD was listed as being addressed in that visit. We will accomplish this by using VINCI data to generate a monthly list of all veterans enrolled in primary care within the VA Palo Alto healthcare system who screen positive on the PC-PTSD screen, which is delivered as part of standard practice, or who have had a recent encounter with PTSD listed as a reason for the visit. This list will include names, Real SSNs, address, phone number, Palo Alto provider name, PC-PTSD raw score and score date, and gender. A list of each individual primary care provider's patients who are identified will be generated and submitted to the provider requesting that they refer these patients to the study. Study staff will send an invitation letter to those patients deemed appropriate for the study by their primary care provider. This letter will be signed by a PACT member introducing the study. Study staff will call referred patients to assess their interest in participation. Interested patients will be scheduled for a baseline appointment within their PC clinic or by telephone to determine study eligibility.

- h) Inclusion and Exclusion Criteria.**

**Identify inclusion criteria.**

Participants will be Veterans enrolled in VA Palo Alto primary care reporting  $\geq 33$  on the PTSD Checklist-5 (PCL-5), which indicates significant PTSD symptoms.

**Identify exclusion criteria.**

**Title :** An RCT of a Primary Care-Based PTSD Intervention: Clinician-Supported PTSD Coach  
**Approval Period:** Draft

Patients will be excluded if they demonstrate symptoms that would not allow them to engage in the CS PTSD Coach (i.e., 1) gross cognitive impairment, 2) current symptoms of mania or psychosis) or who have more pressing concerns needing attention first (i.e., 3) suicide attempt in the last 2 months or current suicidal intent). We will also exclude patients who 4) are already receiving psychotherapy or MH counseling, 5) started or changed psychotropic medication for PTSD in the last 2 months prescribed outside of VA PC, and 6) prefer to be directly referred to MH specialty care.

- i) Describe your screening procedures, including how qualifying laboratory values will be obtained. If you are collecting personal health information prior to enrollment (e.g., telephone screening), please request a waiver of authorization for recruitment (in section 15).**

We will use chart review to identify potential participants. A list of patients who have screened positive for PTSD (using the PC-PTSD screen) in primary care will be generated. A waiver of authorization for recruitment will be obtained for this approach.

During the phone screen (see attachment), potential participants will be informed about whom the study wishes to recruit, including a description of common PTSD symptoms. Potential participants will be asked if they believe they would be appropriate for the study based on whether or not they have those types of symptoms. For those who are not sure, the 4 item PC-PTSD screen will be administered.

- j) Describe how you will be cognizant of other protocols in which participants might be enrolled. Please explain if participants will be enrolled in more than one study.**

We will ask potential participants if they are enrolled in any other research studies that would conflict with their participation in this one. Participants may be enrolled in studies unrelated to this one.

- k) Payment/reimbursement. Explain the amount and schedule of payment or reimbursement, if any, that will be paid for participation in the study. Substantiate that proposed payments are reasonable and commensurate with the expected contributions of participants and that they do not constitute undue pressure on participants to volunteer for the research study. Include provisions for prorating payment. See payment considerations**

Participants will be reimbursed for time spent completing study measures. They will not be reimbursed for attending treatment sessions. They can earn up \$150. Payments will be pro-rated: if the participant completes half of an assessment he/she will be paid half of the amount for that session. The proposed payments are reasonable and would not constitute undue pressure to participate. The payment schedule below reflects a rate of approximately \$20/hour for participation.

Baseline session- \$30

Baseline phone interview- \$20

8 week follow-up- \$20

8 week phone assessment- \$20

16 week follow-up- \$20

24 week follow-up- \$20

Bonus for completing all assessments (and returning a study-owned iPod Touch, if borrowed)- \$20

- l) Costs. Please explain any costs that will be charged to the participant.**

No cost will be charged to participants for their involvement in the study.

- m) Estimate the probable duration of the entire study. Also estimate the total time per participant for: (i) screening of participant; (ii) active participation in study; (iii) analysis of participant data.**

Each participant's total time involvement in the study will be approximately 6 months and involve roughly 6.5 hours of assessments.

The total duration of the study is 4 years. We expect it will take 6 months to hire and train study staff, 33 months to recruit and run participants, and 9 months to complete data entry, analyses, and disseminate results.

**Title :** An RCT of a Primary Care-Based PTSD Intervention: Clinician-Supported PTSD Coach

**Approval Period:** Draft

- a) For the following categories include a scientific estimate of the frequency, severity, and reversibility of potential risks. Wherever possible, include statistical incidence of complications and the mortality rate of proposed procedures. Where there has been insufficient time to accumulate significant data on risk, a statement to this effect should be included. (In describing these risks in the consent form to the participant it is helpful to use comparisons which are meaningful to persons unfamiliar with medical terminology.)

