### Confidentiality Protections

- b) **Specify PHI (Protected Health Information). PHI is health information linked to HIPAA identifiers (see above). List BOTH health information AND HIPAA identifiers. If you are using STARR, use the Data Privacy Attestation to ensure that your request will match your IRB-approved protocol. Be consistent with information entered in section 15a.**

Prospective participants' medical charts will be reviewed to ascertain study eligibility (with a Waiver of HIPAA Authorization for Recruitment). These charts will be evaluated for a positive PTSD screen (PC-PTSD) and whether or not the patient is or will be receiving mental health treatment outside of VA primary care.

If a prospective participant has screened positive for PTSD and is not and will not (i.e., no referral or appointment) be receiving mental health treatment outside of VA primary care, their name, address, and telephone number will be collected from the chart.

**Title :** An RCT of a Primary Care-Based PTSD Intervention: Clinician-Supported PTSD Coach  
**Approval Period:** Draft

Information from the participants' VA administrative data will be extracted regarding date and types of mental health visits they have attended. Information about any new or existing mental health diagnoses (including alcohol or substance use conditions) will be extracted from the progress notes of these visits. Information about the nature of the mental health treatment received (e.g., psychotherapy, medications) will also be collected.

The study will collect information about participants' demographic characteristics (e.g., age, race, ethnicity). Participants' voice will also be audio recorded (during each of the four sessions of Clinician-Supported PTSD Coach and during the telephone-based clinical interviews). Finally, IIHI will also be collected during the study using self-report questionnaires and interviews.

Finally, participants' email address and survey data will be collected and stored using Stanford University School of Medicine's REDCap system (see 9. Risks, c).

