**Table of Measures**

Measure	Construct	0 wk	8 wk	16 wk	24 wk
Blessed Orientation Memory Concentration	Cognitive Impairment	X			
Demographics & Military Background	Demo & Military Service	X			
Columbia-SSRS	Suicidal Ideation	X	X	X	X
Alcohol Use Identification Test (AUDIT)	Alcohol Use	X	X	X	X
Drug Abuse Screening Test (DAST)	Drug Abuse	X	X	X	X
Clinician Administered PTSD Scale-5 (CAPS-5)	PTSD (interview)	X	X		
VA Administrative Data	Treatment Engagement	X			X
Client Satisfaction Questionnaire (CSQ)	Treatment Satisfaction		X		
Patient Feedback Interviews	Patient Feedback		X		
Coping Self-Efficacy Scale	Coping Self-Efficacy	X	X	X	X
Patient Health Questionnaire-9 (PHQ-9)	Depression	X	X	X	X
WHO QOL-BREF	Quality of Life	X	X	X	X
PTSD Checklist-Specific-5 (PCL-5)	PTSD (self-report)	X	X	X	X

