The objective of Aim 2 is to correlate treatment arm with engagement in specialty MH care. We will evaluate the effect of the CS PTSD Coach condition on rate of attendance to at least 2 specialty MH visits post randomization (week 1 to week 24). To evaluate whether rates of attendance differ by condition, we will fit a mixed effects logistic regression model with a subject-specific random effect, an indicator for condition, and indicators for each time point. We are particularly interested in the effect of condition at 24 weeks. The parameter of interest, therefore, is the interaction term that corresponds to rate of treatment attendance at 24 weeks.

Several approaches will be used to evaluate our Exploratory Aims. To explore potential mediators (i.e., amount of app use, improvement in coping self-efficacy), we will fit 2 models for each potential mediator. One will include condition only and the second will include condition and the potential mediator. Change in the coefficient corresponding to condition after inclusion of the mediator may indicate a mechanism of action. To examine possible moderators (e.g., baseline PTSD severity), interaction terms between possible moderators and condition will be assessed. Significant interaction terms will suggest that the effect of intervention varies by

levels of the moderator. Lastly, to evaluate symptom trajectories over time, we will consider a mixed effects model of PCL scores at all time points with indicators for each follow-up visit (at 8, 16, and 24 weeks), randomization group, and an interaction between the indicators for time and condition as represented by the 3 product terms. A test evaluating all 3 product terms will address whether CS PTSD Coach affects the overall trajectory of PCL score. We will also explore if trajectories are moderated by continued PTSD Coach use and receipt of MH treatment. A similar approach proposed to test Aim 1 will be used to determine if CS PTSD Coach has broader effects, beyond PTSD symptom improvement, on depression and quality of life.

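### Protocol sections 8(h) and 11(b) state different prior-treatment rules, and the Aim 2 model names no term for specialty mental health use before randomisation

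*Protocol*

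**What the plan says.** **Eligibility list.** Protocol section 8(h) excludes patients who "are already receiving psychotherapy or MH counseling", who "started or changed psychotropic medication for PTSD in the last 2 months prescribed outside of VA PC", or who "prefer to be directly referred to MH specialty care". Section 2(a) gives the same criteria in substance.

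**Chart review.** Protocol section 11(b), under Confidentiality Protections, says that charts of prospective participants are reviewed to establish eligibility. One item checked is "whether or not the patient is or will be receiving mental health treatment outside of VA primary care". Contact details are then taken from the chart only if the patient screened positive for PTSD and "is not and will not (i.e., no referral or appointment) be receiving mental health treatment outside of VA primary care".

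**Recruitment routes.** Section 8(g) lists two. One is chart review. The other is "Direct in person referral from clinical staff on the patient's health care team (PACT) in the primary care setting". That section does not mention the section 11(b) condition for either route.

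**Endpoint and model.** The SAP's Design and Methods Overview makes engagement in specialty MH care a primary outcome. For Aim 2, its Data Analysis section specifies the "rate of attendance to at least 2 specialty MH visits post randomization (week 1 to week 24"). The model is a mixed effects logistic regression with a subject random effect, condition and time indicators. The parameter of interest is the interaction at 24 weeks.

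**Baseline data.** The SAP's Table of Measures marks "VA Administrative Data", the treatment-engagement measure, at weeks 0 and 24. The SAP does not say how the week-0 data enter the analysis, and it restates neither prior-treatment rule.

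**The concern.** Read alone, the numbered exclusions leave two kinds of patient eligible: a Veteran on a stable regimen followed by specialty MH, and one already referred or booked there but not yet seen. Section 11(b) would screen out both. It would also leave the medication exclusion with little to do, because a patient whose PTSD medication was recently started or changed by a prescriber outside VA primary care would usually be in MH treatment outside primary care already. The two sections therefore do not describe the same population.

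This bears on a primary outcome. The Aim 2 endpoint has no look-back and does not separate continuing care from care that began after randomisation. If some participants had specialty care under way or pending, part of the count in each arm would be visits that the trial did not prompt. That would raise both rates, could shrink the difference between arms, and would blur what engagement means. The data that could deal with this appear to be available at week 0, but the SAP assigns them no role.

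**Working it through.** **The two rules side by side**

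| Patient at screening | Section 8(h) list | Section 11(b) chart review |
|---|---|---|
| In psychotherapy or counseling outside VA primary care | Excluded | Screened out |
| Medication for PTSD started or changed within 2 months by a prescriber outside VA primary care | Excluded | Screened out if this is MH treatment outside primary care |
| Stable medication followed in specialty MH | Not mentioned | Screened out |
| Existing specialty referral or appointment | Not mentioned | Screened out |

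Both sections come from the Palo Alto application. The Continuing Review Form, item 1(a), reports 70 participants eligible for randomisation at Palo Alto and 164 at Syracuse. So 164 of 234 (70%) come from a site for which neither document states the prior-treatment rule separately.

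**The plan's own binary figure.** The SAP gives no power statement for Aim 2. It says that a 20-point difference is detectable for clinically significant outcomes, with 15% loss (130 × 0.85 = 110.5, stated as 110 per arm). A two-proportion z-test at two-sided 0.05 with 110 per arm gives power of 96.4%, 90.5%, 86.2% and 84.8% for control rates of 10%, 20%, 30% and 40%. The SAP's figure is reproduced and is slightly conservative.

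**Effect of prior or pending care**

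Inputs:
- 118 TAU and 114 CS PTSD Coach participants (Continuing Review Form, item 1(a)); two-sided alpha 0.05 (SAP, Power Analysis).
- Assumed, because the documents do not give them: the share *f* with specialty care under way or pending, the attendance rates *a* in that group, and the rates *q* in everyone else. The base case is *q* = 20% versus 40%.

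Formulas:
- Rate in each arm: p = f·a + (1 − f)·q
- Power = Φ[(|Δ| − 1.96·s0)/s1], where s0 = √[p̄(1 − p̄)(1/118 + 1/114)] and s1 = √[p_TAU(1 − p_TAU)/118 + p_CS(1 − p_CS)/114]

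Example with f = 10% and everyone in that group attending in both arms:
- p_TAU = 0.10 + 0.90 × 0.20 = 0.28; p_CS = 0.10 + 0.90 × 0.40 = 0.46; Δ = 0.18
- p̄ = (118 × 0.28 + 114 × 0.46)/232 = 0.3684; s0 = 0.06335; s1 = 0.06235
- Power = Φ[(0.18 − 1.96 × 0.06335)/0.06235] = Φ(0.896) = 81.5%

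| f | All attend in both arms: difference, odds ratio, power | 60% attend in both arms: power | 50% vs 70% attend: power | Group removed: power |
|---|---|---|---|---|
| 0 | 20 points, 2.67, 91.9% | 91.9% | 91.9% | 91.9% |
| 5% | 19 points, 2.39, 87.1% | 88.1% | 91.2% | 90.5% |
| 10% | 18 points, 2.19, 81.5% | 83.5% | 90.5% | 88.9% |
| 20% | 16 points, 1.93, 69.2% | 72.2% | 89.3% | 85.1% |

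The last column uses 118(1 − f) and 114(1 − f) at 20% versus 40%. With 30% versus 50% in everyone else and full attendance in the group, power is 88.0%, 83.7%, 78.9% and 68.6%. Unpooled variance moves the results by about one point (for example 82.3% instead of 81.5%). The test is a simple stand-in for the SAP's mixed logistic model.

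The loss therefore depends on two unknowns: how large the group is, and whether treatment also affects its attendance.

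**The case against.** A reader might infer that the protocol admits patients already in specialty care and that Aim 2 counts their visits as new engagement. The documents do not support that. Section 11(b) describes the chart review as a check on study eligibility and speaks of prospective participants without limiting the recruitment route. The recruitment waiver in section 15.1 covers referrals from primary care staff and lists MH treatment history. The review may thus have been applied to everyone, leaving *f* near zero. The SAP speaks of attendance after randomisation and never calls it new. What stands is that the two sections differ and that the SAP does not say which rule defined the sample at either site.

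A reader might also take the largest power losses as the expected result. They require that everyone in the group attends whatever the arm. Section 1(a) says that many patients decline referrals or do not engage adequately, so turning a referral into visits is part of the question. Section 2(a) also has CS PTSD Coach participants who still score 33 or more on the PCL-5 at session 4 recommended for specialty treatment, so the intervention could change attendance in this group too. This objection is sound. It makes the large losses an upper-end scenario, and it argues against replacing the all-randomised primary population with a subset.

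Finally, the interaction parameter and the week-0 administrative data suggest that some baseline reference was intended. That may be so, but the endpoint is defined only after randomisation and no baseline value is specified, so the model as written does not supply one.

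**Conclusion.** The concern holds as an unresolved inconsistency in eligibility combined with an Aim 2 model that leaves an available baseline variable unused. It is not shown that patients in specialty care were enrolled. Randomisation balances prior users in expectation, so neither type I error nor the direction of the comparison is threatened. What is at risk is attenuation, precision and the meaning of the endpoint.

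The size cannot be established from the documents. For *f* of 5% to 20%, and with 20% versus 40% in everyone else, the loss from 91.9% power runs from under 3 points (50% versus 70% attendance in the group) to about 23 points (full attendance in both arms at f = 20%). It is negligible if the section 11(b) review covered everyone. The change is worth making because it costs little and settles the question from data already planned.

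**What to change.** - **Population.** Keep all randomised participants as the primary Aim 2 population.
- **Covariate.** Before analysis, fix a look-back period, derive specialty MH use before randomisation from the week-0 VA administrative data, and add it to the Aim 2 model. If it nearly determines the outcome, an ordinary logistic fit can fail to converge, so specify a penalised fit or a standardised risk difference in advance.
- **Reporting.** Give the frequency of prior use by arm. This alone shows whether the issue matters.
- **Sensitivity analysis.** Repeat Aim 2 in participants with no specialty MH visit in the look-back and no open referral or appointment at baseline. All of these precede randomisation, so the restriction does not bias the comparison.
- **Eligibility text.** Reconcile Protocol sections 8(h) and 11(b), and state in the SAP the single prior-treatment rule that describes who was eligible at both sites.

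Cost: one derived variable, one extra analysis and some wording. Two limits should be stated. VA data may miss visits outside VA. The protocol describes extracting the dates and types of visits attended, so open referrals or appointments may have to come from the chart review.
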